The recruitment and screening period for potential participants will be 12 months (in order to identify 70 eligible participants) following the decision to initiate the protocol. It is expected that 70 participants will be informed and consented, and enrolled in the study, by approximately 12 months. Treatment for each participant will be carried out for a total of 9 months, or less if there is evidence of clinical

CONFIDENTIAL

and mycological cure prior to that time. The 9-month follow up visit will serve as the primary efficacy endpoint, in keeping with the usual expected minimum 7 to 9 -month duration of time expected for a full replacement of the visible nail plate in a typical adult human. Thereafter, a 3-month period will be allotted for completion of mycological testing and data collection. An additional 3 months will be allotted for completion of the analyses and 3 more months to write the report describing the study and submission of the manuscript for consideration for publication in a refereed journal. It is, therefore, estimated that the duration of time necessary for the completion of this protocol, data analysis, and preparation of the final report, will be approximately 35 months.

Study Centers

This study will be carried out at multiple clinical offices, under the guidance of different CITI-trained investigators, including:

- [name], DPM; Ankle & Foot Associates, [contact] (cell) Contact: Self; [contact], [name]. Site A
- [name], DPM; St Cloud Foot & Ankle; [contact] (cell) Contact: self; [contact] [name]. Site B
- [name], DPM; National Foot and Ankle, [contact] (cell) Contact: Self; [contact], [name]. Site C
- 4. [name], DPM; Family Foot Care, [contact] (cell) Contact: Self; [contact], [name]. Site D
- [name], DPM (the Principal Investigator); Foot & Ankle Specialists of Nevada, [contact] (cell) Contact: Self; [contact], [name]. Site E
- [name], DPM; A Step Ahead Foot and Ankle, [contact] (cell) Contact: Self; [contact], [name]. Site F
- [name], DPM, [name], DPM; The Division of Podiatry at The GW Medical Faculty Associates, [contact]) Contact: Office; [name]. Site G.

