Table 1 Topical solution tube site-participant designation*

CONFIDENTIAL

A4	B4	C4	D4	E4	F4	G4	H4	J4
A5	B5	C5	D5	E5	F5	G5	H5	J5
A6	B6	C6	D6	E6	F6	G6	H6	J6
A7	B7	C7	D7	E7	F7	G7	H7	J7
A8	B8	C8	D8	E8	F8	G8	H8	J8
A9	B9	С9	D9	E9	F9	G9	H9	J9
A10	B10	C10	D10	E10	F10	G10	H10	J10
An	Bn	Cn	Dn	En	Fn	Gn	Hn	Jn

*This designation correlates with the randomization schedule and enables the principal investigator to keep track of active and placebo distribution and use.

A study coinvestigator, not participating at a study site, and not tasked with data analyses, will maintain the random allocation code, which will contain this same information as well as the randomly allocated topical solution, denoted as either the placebo nail solution or the active topical nail solution.

Inclusion and Exclusion Criteria

Inclusion criteria for participation in this study include:

- 1. Male or female participants aged 18 years or older;
- 2. If female is of childbearing potential, she must not be pregnant at the time of enrollment and she must be using an accepted form of birth control during the study treatment period (acceptable forms include: postmenopausal, surgical sterility, complete abstinence, sterilized sexual partner, tubal occlusion, copper-T intrauterine device, levonorgestrelreleasing intrauterine device, medroxyprogesterone injections, etonogestrel implants, combined pills, norelgestromin/ethinly estradiol transdermal system, intravaginal device, or Cerazette pill; and for males the use of a condom with spermicide or surgical sterility);
- 3. Participant has a diagnosis of onychomycosis diagnosed by means of history, physical examination, and positive (evidence of fungal hyphae) mycological tissue examination by periodic acid-Schiff (PAS) staining;
- 4. At least one toe nail with distal subungual involvement, localized to any toe, with at least 10% involvement and including up to 100% involvement of the visible nail plate, any nail plate thickness, with the index nail being the most involved per inspection by the on-site investigator and agreed upon by the designated co-investigator study doctor ([name], DPM), who will inspect specific clinical photographs of the involved nail/s (the photographs will be obtained at each study site using a specified method, as demonstrated to site investigators, so that the clinical features are appropriately demonstrated);

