After enrollment into the study, participants will be randomly allocated to either the placebo nail solution or the active topical nail solution. Randomization will be carried out by means of electronic random number generation under the authority of a co-investigator ([name]), who will prepare sealed, sequentially numbered envelopes for each study site, and mail the envelopes to the designated coordinator for each study site (A-J) (Table 1). In each sealed envelope will be a tube of the topical solution, either the active topical nail solution or the placebo nail solution, consistent with the random number list, which will determine whether or not the placebo or active topical nail solution is contained in the tube. Each tube will be numbered in sequential numeric order from 1 to n, and recorded in the investigator's master list, which will serve to record the random allocation code, detailing whether or not the placebo nail solution or the active topical nail solution was dispensed in the designated tube. Furthermore, each block of tubes will be designated with a letter, A to J, to represent the distinct study sites. The labeled tubes will be mailed to the study sites in blocks of 10, and replenished based on the prevalence of enrolment at each site. At each study site, the investigator will open, in sequential numeric order, a sealed envelope and dispense the labeled tube to the eligible participant in consecutive order. Neither the study doctors responsible for assessing the results of the intervention, nor the participants themselves, will know which of the treatment groups the participant will be in (until after completion of the analyses, when the randomization code will be revealed if a participant or investigator desires to know, and participants randomized to the placebo group will also have the opportunity to receive, from the study sponsor, and free of charge, a course of the active topical nail solution with the Tolcylen™ Fungal Eradication Nail/Skin Renewal Kit, which includes Tolcylen™ Antifungal/Nail Renewal Solution, Tolcylen[™] Antifungal Skin Cream, and Tolcylen[™] Antimicrobial Shoe Spray (up

CONFIDENTIAL

to 2 kits)). The nail solution with its envelope will be stored in a secure medicine supply cabinet or at the site investigator's office at a secure location.

Diagnosis of Primary Outcome

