Study Product, Dose, Route and Regimen

All participants will be undergoing one of two interventions. Participants in the control group will apply the placebo nail solution to the involved toenail/s. Preparation of the placebo nail solution (dimethicone 5%, a skin protectant and emollient) was undertaken with the aim of making it as close as possible to the active treatment agent in terms of color and texture, and the gross physical

CONFIDENTIAL

Efficacy of Topical Active Nail Solution versus Placebo Nail Solution Alone Principal Investigator: [name], DPM Sponsor: Marlinz Pharma

appearance of the solution. The placebo nail solution, like the active topical nail solution, meets the FDA's safe ingredient criteria for an over-the-counter topical agent. The placebo nail solution, like the active topical nail solution, will be supplied in three (3) 7.5 ml tubes with a controlled-release applicator mechanism that allows thin coat of the solution to be applied at a time, and the instructions for application specify that only thin coat of solution to be applied daily to under the leading edge, borders of the toenail and the entire surface of the toenail. It is expected that use of the controlled-release applicator tube will last on average 4 to 5 months when used on two toenails, and therefore each participant will be provided with three (3) tubes of the randomly allocated solution as needed during each follow up visit of their participation in the investigation. The tube containing the topical solution is also designed to prevent evaporation of the agent, and the base terminal of the tube will have a crimped seal labeled with an imprinted code that designates the ingredient as either placebo or active topical solution contained in the tube. Three tubes will be dispensed in order to provide enough of the randomly allocated solution to minimize the potential need to supply more product. If a tube is lost by the participant, or if for any reason the participant runs out of the randomly allocated topical solution, then the PI will ascertain the precise agent (placebo or active topical nail solution) and a replacement tube (also with the base terminal of the tube labeled with an imprinted code that designates the ingredient contained in the tube as either placebo or active topical solution) of the randomly allocated topical solution will be forwarded directly to the study site and dispensed to the participant.

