Within the following 48 hours, the investigator must provide further information on the serious adverse event in the form of a written narrative. This should include a copy of the completed Serious Adverse Event form, and any other diagnostic information that will assist the understanding of the event. Significant new information related to an ongoing serious adverse event should also be provided promptly to the study sponsor.

• EC/IRB Notification by Investigator

Reports of all serious adverse events (including follow-up information) must be submitted to the EC/IRB (ethics committee/ institutional review board) within 10 working days. If the serious adverse events involved death must be submitted to the EC/IRB within 3 working days. Copies of each report and documentation of EC/IRB notification and receipt will be kept in the Clinical Investigator's binder. Serious adverse events will be reported by Email or phone and facsimile to:

> [name] | IRB Operations Specialist WCG IRB [name] o/ [contact] d/ [contact] (Eastern Time) [contact] | www.wcgirb.com

CONFIDENTIAL

Unblinding Procedures

It is not likely that any AE or SAE will develop in relation to this study, since the intervention in question is already an established method of treatment of pedal dystrophic toenail, with a longstanding record of safety and widespread use in the United States. If, however, an adverse event develops in a participant, wherein there is serious risk of morbidity or mortality, there is no conceivable way that knowing whether or not the participant received topical active nail solution or placebo nail solution will make any difference in the management of the participant. If, however, it becomes necessary to unblind a blinded treating doctor or study staff member, this responsibility lies with the Principal Investigator and the Sponsor charged with oversight of the research investigation. The Blind Randomization Schedule Master List for this protocol (Marlinz Pharma #IIT-6042-04-002) will be secured by a co-investigator ([name]), and in the Office of Scientific and Medical Affairs, at;

> Marlinz Pharma [name] [contact]

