This information will remain only with these two individuals, the coinvestigator ([name]) and the science officer, or his/her direct appointee assigned to this task and will not be accessible to any clinical researchers employed at Marlinz Pharma. Moreover, the secured information will not be available to investigators or participating clinical sites during the extent of the investigation, with the exception of the member of the investigational team responsible for assuring that participants are assigned to the appropriate treatment group (in accordance with the randomized allocation schedule), namely the coinvestigator ([name]). In the event of an emergency, the investigators may contact:

[name], DPM [name] Penn Presbyterian Medical Center [name] [contact]

[name] Marlinz Pharma [name] [contact]

If there is a need to obtain the Blind Schedule, prior authorization will be required. The decode procedure for blinding will be strictly adhered to. Unblinding will be documented in the source documents and CRFs, and notification of the sponsor will take place within 24 hours by Email, text

CONFIDENTIAL

message or telephone or telefax, followed by a written narrative of the event within 48 hours.

Data and Safety Monitor (DSM)

This study will be monitored by a Data and Safety Monitor, should any adverse or serious adverse events arise. The details of the organization and operation of the DSM are described in Attachment 9, appended to this protocol.

Stopping Rules

It is not anticipated that this study will impart a high or unreasonable risk to the participants. Nonetheless, a Data Safety Monitor (DSM) will have oversight of the progress and make recommendations related to participant safety and progress. The DSM will have the authority to dictate stopping rules, based on his/her analysis of the results of the study at predetermined times along the course of the investigation. The details of the organization and operation of this DSM are described in Attachment 9, appended to this protocol.

Medical Monitoring

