Any investigator who has a conflict of interest with this study (patent ownership, royalties, or financial gain greater than the minimum allowable by their institution, etc.) must have the conflict reviewed by a properly constituted Conflict of Interest Committee with a Committee-sanctioned conflict management plan that has been reviewed and approved by the study sponsor prior to participation in this study. All investigators will follow the organization's conflict of interest policy. Attachment 12 is the Conflict-of-Interest Disclosure (COID) form to be used by all members of the investigation team.

Participant Stipends or Payments

Participants will not receive any monetary remuneration for participation in this study. There is no participant stipend or payment for participation in this research project. Participants randomly allocated to the placebo arm of the study will have the option to receive the active topical nail solution, Tolcylen[™] for up to nine months (or two 7.5ml tubes), Tolcylen[™] Antifungal Skin Cream, and Tolcylen[™] Antimicrobial Shoe Spray (up to 2 kits), provided by the study sponsor free of charge, with instructions as to proper use. This option will be described to potential participants during the informed consent process.

Study Site Stipends or Payments

Each study site coinvestigating director will be paid \$300.00 by the study sponsor, Marlinz Pharma, for each participant enrolled that completes 7-9

CONFIDENTIAL

months study at each study site. This payment is aimed at reimbursing the site director and his/her staff for the work required to appropriately conduct this clinical experiment in accordance with United States and International Standards of Good Clinical Practice (FDA Title 21 part 312 and International Conference on Harmonization guidelines), applicable government regulations, and institutional research policies and procedures.

The principal investigator and statistician-coinvestigator will be paid by the study sponsor, Marlinz Pharma, \$43,750 to oversee the execution of this clinical trial, to analyze the data, and to prepare a written report of the findings with the intention of submitting the final report to a peer-reviewed journal for consideration for publication.

Publication Plan

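### The replacement-tube rule gives allocation to the Principal Investigator, the only investigator listed for Site E, against the protocol's own restriction on the code

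*Protocol*

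**What the plan says.** **Duties given to the PI**
- Protocol, Study Product, Dose, Route and Regimen, on a tube that is lost or runs out: "then the PI will ascertain the precise agent (placebo or active topical nail solution) and a replacement tube". The replacement is then sent to the site and dispensed.
- Protocol, Study Population, footnote to Table 1: the site-participant designation "enables the principal investigator to keep track of active and placebo distribution and use".

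**The PI's place in the trial**
- The Study Summary and the Study Centers section both list the PI as a site investigator. The Site E entry reads "DPM (the Principal Investigator); Foot & Ankle Specialists of Nevada", and no second investigator is listed there.
- Inclusion criterion 4 has the on-site investigator pick the index nail, with a designated co-investigator agreeing from photographs. Method for Assigning Participants to Treatment Groups has the site investigator open the envelopes and dispense.

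**Restriction on the code**
- The paragraph after Table 1 gives the code to a coinvestigator who is at no study site and does not analyse the data.
- Unblinding Procedures adds a sponsor science officer or appointee and says "the secured information will not be available to investigators or participating clinical sites during the extent of the investigation". That coinvestigator is the only exception on the investigational team.

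**Assessor blinding**
- Method for Assigning Participants: "Neither the study doctors responsible for assessing the results of the intervention, nor the participants themselves, will know" the treatment group.
- Research Design and Methodology requires blinded assessors for all clinical and mycological examinations. The follow-up paragraph under Study Product, Dose, Route and Regimen has a blinded investigator see the participant. The section on the Visible Nail Plate Involvement Score (VNPIS) has the nail rated by a blind site investigator or, from a photograph, by blind coinvestigators.

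**The concern.** The protocol presents blinded outcome assessment as a distinguishing feature of this trial (Relevance of this Study; Research Problem). The replacement rule hands a participant's arm to someone who recruits and dispenses at a site and is the only clinician named there.

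Once the arm is known, later judgements about that participant are open to influence. The VNPIS rates gross appearance, and study staff may decide to discontinue a participant. The final periodic acid-Schiff (PAS) test falls at 3, 7 or 9 months depending on when the intervention ends. A laboratory reads the slide, which protects the reading but does not blind the clinic.

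**Working it through.** The point rests on comparing roles. No figure of the plan is in dispute.

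**1. Does the PI learn the arm?** Under the replacement rule, yes. It names the PI and says that what is ascertained is whether the agent is active or placebo. The Table 1 footnote points the same way but is loosely worded.

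**2. May the PI have this information?** No. Unblinding Procedures limits it to two holders, the coinvestigator and the science officer or appointee, and excludes investigators and sites. The coinvestigator qualifies by being at no site. The PI is at Site E and so cannot be that person.

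**3. Does another rule repair it at Site E?** Only in part. The protocol requires a blinded investigator at follow-up, but the sole investigator listed for Site E is the person given the look-up. Photograph scoring by blind coinvestigators is available as an alternative and is not required.

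**4. Who is affected?** The look-up is made per participant, after that participant's nail has been chosen and the first tube dispensed. The direct exposure is therefore Site E participants who lose or use up a tube, from that moment on.

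**5. How large is Site E?** Its enrolment is not stated. With 70 participants and equal enrolment (an assumption):
- nine listed sites (A to H and J): 70/9 = 7.8 participants, 1/9 = 11%
- six sites, the number in Power and Sample Size Determination: 70/6 = 11.7 participants, 1/6 = 17%

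**6. How often would a look-up happen?** The protocol says a tube lasts 4 to 5 months on two nails, which is 8 to 10 nail-months. Three tubes give 3 × 8 = 24 to 3 × 10 = 30 nail-months. Treatment lasts up to 9 months.
- If three tubes are the whole supply: two nails, 24/2 to 30/2 = 12 to 15 months; three nails, 24/3 to 30/3 = 8 to 10 months; four nails, 24/4 to 30/4 = 6.0 to 7.5 months.
- If three tubes are given at baseline and again at each visit (3 and 7 months), the longest gap is 7 − 3 = 4 months, and the supply covers 24/4 to 30/4 = 6 to 7.5 nails.

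The text says tubes are provided as needed at follow-up visits, which leaves both readings open. It gives neither the number of involved nails per participant nor a rate of tube loss. No frequency follows.

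**The case against.** The strongest reply is that the protocol requires blinding where it counts. Follow-up is with a blinded investigator, the nail score is given blind, a laboratory reads the primary endpoint, and the look-up is conditional and limited to one participant at a time. Look-ups for other sites do not tell the assessors there anything. All of this stands, and it limits the size of the problem. It does not remove the contradiction, because the person given the look-up is the only investigator named at one site.

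A reader might infer more than the text supports:
- **That Site E is rated and sampled unblinded.** No section says so. The rating rules say the opposite, and the document does not state who takes the nail specimen.
- **That the PI holds the decoded list, so that concealment fails at Site E.** The sentence after the Table 1 footnote says the coinvestigator's code holds the same information plus the allocated solution. This indicates that the designation alone does not reveal the arm.
- **That decoding would be common.** This needs three tubes to be the total supply, which the text does not settle.
- **That the PI analyses data unblinded.** The payment "to oversee the execution of this clinical trial, to analyze the data, and to prepare a written report of the findings" is made jointly to the PI and the statistician-coinvestigator, and Statistical Methods keeps the statistician blind with arms labelled A and B.
- **That emergency unblinding also gives the PI the arm.** The text says only that "this responsibility lies with the Principal Investigator and the Sponsor charged with oversight of the research investigation". It does not say that the PI receives the allocation.

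**Conclusion.** The contradiction is real and should be reconciled. If the replacement rule is followed as written, a recruiting and dispensing site investigator learns the arm of at least those Site E participants who need a replacement tube. The code restriction and the assessor blinding then do not hold for them, and no separate blinded assessor is named for that site.

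The number affected is a subset of Site E's enrolment and cannot be computed from the document. Site E itself is about 8 of 70 (11%) if nine sites enrol equally and about 12 of 70 (17%) if six do. Both shares are assumptions. No size of bias can be given. The VNPIS is the more exposed outcome if the PI does the rating. An effect on the laboratory-read PAS result would need a clinic role in sampling or timing that the document does not assign to the PI.

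**What to change.** 1. **Study Product, Dose, Route and Regimen:** have the site request a replacement by participant number from the code-holding coinvestigator. That person identifies the agent and ships the tube without disclosing the arm to the PI or the site.
2. **Footnote to Table 1:** make the code-holder, not the PI, the person who tracks active and placebo distribution.
3. **If the PI has already seen the allocation of any Site E participant:** have that participant's index nail scored from photographs by the blind coinvestigators. The VNPIS section already allows this, and photographs are already part of the follow-up visit.

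The cost is rewording in two places, plus photograph scoring for any participant already affected. The code-holder already exists, so no staff are added. Sample size, visits and treatment do not change.
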